5.3 Subject Recruitment

Part 1: Subjects will be recruited with IRB approved recruitment materials

Part 2: Subjects admitted to Penn Presbyterian Medical Center will be screened by [REDACTED] for eligibility within the first 24 hours of admission.

5.4 Duration of Study Participation

Part 1: The duration of study participation will continue for a maximum of 3 hours.

Part 2: The duration of study participation will continue for 6 consecutive hours.

5.5 Total Number of Subjects and Sites

Part 1: Recruitment will end after 3 subjects have been enrolled.

Part 2: Recruitment will end when no fewer than fifteen (15) evaluable subjects and no greater than twenty (20) evaluable subjects have completed the clinical protocol. In the event a subject begins the clinical protocol, however, does not meet protocol defined requirements of "evaluable" status (see section 9.2, Part 2), the Sponsor reserves the right to replace that subject, which may result in greater than twenty (20) subjects being enrolled. In the unlikely event a disproportionate number of enrolled subjects do not meet the protocol defined requirements for reaching "evaluable" status, the Sponsor may pause the study to enrollment to reevaluate recruitment, inclusion and/or exclusion, or any other activity deemed necessary at the time.

5.6 Vulnerable Populations

Vulnerable populations are not included in this study.

6 STUDY INTERVENTION; OSCIPULSE DEVICE

6.1 OsciPulse Description

The OsciPulse device consists of a wearable calf band that contains an inflatable air bladder, and is wrapped around the patient's calf.

[REDACTED]

[figure not shown]
[figure not shown]

Figure 2 OsciPulse Device

6.2 Intervention Regimen

Part 1: The OsciPulse device will be worn by the subjects while they are in bed during the study duration. The subjects will be permitted to get up to use the restroom and for periods of stretching or walking for their comfort but will be encouraged to remain in bed for most of the study time. The device will be removed and reapplied by a clinical research coordinator or other trained personnel.

Part 2: The OsciPulse device should be worn by the subjects any time that they are in bed or seated in their room during the assigned 3-hour period. During operation, the device will inflate, compressing the calf 4-6 times per minute. The device will be worn during periods of subject immobility, including while sleeping. The device will be removed if the subject is getting out of bed and is ambulatory, or if the subject is receiving clinical care that requires that the device be removed as dictated by the clinical care team.

6.3 Receipt

Both the head units and wearable bands will be received from [REDACTED], who will oversee device manufacturing and quality assessment prior to shipping. Instructions for use will ship with each head unit and wearable band. Both head units and calf bands will be supplied by [REDACTED] in sufficient quantities to complete the study.

6.4 Storage

The head unit with air tubing and wearable bands of the OsciPulse device will all be stored in the [REDACTED] office in the [REDACTED] at Penn Presbyterian Medical Center when not in use. The devices will be kept at room temperature in a locked cabinet. The head units will be initially wrapped in plastic, and in between uses the head units will be wiped with antiseptic wipes before storage and again after removal from storage. The wearable bands will be stored in the manufacturer packaging for single use.

6.5 Preparation and Packaging

Preparation of the device will be limited to the head unit being removed from a storage box or locked cabinet and hung from the end of the hospital bed and plugged into a standard power supply. A set of air tubing (2 pieces) will be delivered with the head unit in sealed plastic and should be kept together with the head unit between uses. The wearable calf bands will be removed from their sealed plastic bag packaging and strapped onto the legs of the subject. Instructions for Use will be provided to each subject.

6.6 Blinding

The intervention will not be blinded in this study

6.7 Administration and Accountability

The OsciPulse Instructions for Use will be provided to each subject and available in room for clinical staff. In summary, to administer the OsciPulse device, the calf bands will be fitted to the subject's calf with the aim to be snug without being too tight to restrict blood flow. [REDACTED]
[REDACTED].
[REDACTED]

[REDACTED] The clinical staff applying the device should confirm the first inflation to ensure that the device is set up correctly.

A pair of calf bands will be used for each subject, and at the end of the 3-hour period the bands will be disposed of in the hospital waste stream. The head unit can be wiped down with antiseptic wipes and returned to central storage along with the tubing.

The [REDACTED] staff will maintain accountability records for both the head units and the bands. The accountability log will include the following:

- the date of receipt of each item
- the unique identifiers of each item
- the date each device is distributed
- the protocol defined subject number to which each device was assigned
- Date of return or destruction

6.8 Product Problems and Complaints

The study staff will record any product problems and complaints on the IP Quality Complaint form and notify [REDACTED] and the Sponsor according to section 10.4.3.

6.9 Return or Destruction of Investigational Product

Wearable bands used on subjects will be disposed of in the hospital waste stream upon completion of the 3-hour period of use. The head units and unused bands will be picked up by [REDACTED] at the completion of the study.

7 STUDY PROCEDURES

Figure 3 Schedule of Study Procedures

Part 1:

Study Phase	Enrollment / Screening	Intervention and Assessment		
		-0.5 hrs	0 – 3 hrs	3 hrs
Screening and enrollment:				
Informed Consent	X			
Demographics	X			
Review inclusion/exclusion criteria	X			
Intervention				
OsciPulse device		X		
Assessment				
Ultrasound scan				X
Adverse Event Monitoring	X	X		X
Compliance Monitoring				X
Questionnaire				X

Part 2:

Study Phase	Enrollment / Screening	Intervention and Assessment				
		- 24 hrs	0 – 3 hrs	3 hrs	3(+/-1) – 6 hrs	6 hrs
Screening and enrollment:						
Informed Consent	X					
Review inclusion/exclusion criteria	X					

Study Phase	Enrollment / Screening	Intervention and Assessment			
		- 24 hrs	0 – 3 hrs	3 hrs	3(+/-1) – 6 hrs
Study Hour					
Demographics	X				
Laboratory Test Results		X			
Medical Record Review and History	X				
Vital Signs: BP, HR, RR	X				
Height and Weight	X				
Randomization of treatment sequence	X				
Intervention (Group A):					
OsciPulse device		X			
IPC device				X	
Intervention (Group B):					
IPC device		X			
OsciPulse device				X	
Assessment:					
Compliance monitoring*			X		X
Adverse Event Monitoring	X		X		X
Questionnaire(s)			X		X
Hemodynamic ultrasonography (when feasible)		X		X	

*Inquire with subject if the device was removed during the testing period

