1.2 Schema

Figure 1. Study Schema

PART 1:

Visit 1

Total Subjects 3: Consent eligible participants

Visit 1

OsciPulse application and study procedure (3 hours)

Proceed from Part 1 to Part 2 if all subjects indicate a lack of “significant discomfort” during Part 1

PART 2:

Visit 1

Total Subjects up to 20: Screen, consent, and randomize eligible participants (within 24 hours from hospital admission)

Visit 2

Intervention 1 and study procedures (0-3 hours)

Visit 3

Intervention 2 and study procedures (3-6 hours)

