4.4 Allocation to Interventional Group

All enrolled subjects will be assigned to both interventions. [REDACTED] will allocate the treatment sequence groups (group A: OsciPulse then IPC and group B: IPC then OsciPulse) in a 1:1 ratio by using block randomization. Prior to the study launch, [REDACTED] will create 4 envelopes. Each envelope will contain a GreenPhire card that will contain subject compensation, and a randomization form for either group A or for group B. This group of 4 envelopes will maintain the 1:1 ratio of randomization to group A or group B. Once all 4 envelopes have been sealed, they will be shuffled so that none of the research team knows which envelope contains each randomization form. Once the envelopes have been shuffled, the [REDACTED] study team member will place them in a random order and write subject study ID number on the outside of the envelope, indicating which subject they will be used for. For the first group, this will generate randomization for subjects one through four. When a subject is enrolled, the subject will be assigned a study identification number and the CRC will select the envelope with corresponding study-ID number—this will serve as the patient randomization. This process will be repeated 4 additional times in order to provide randomization for subjects 5 – 20. Once the envelope has been selected, the study team member will open the envelope, deliver the GreenPhire card to the subject and record the subject's intervention group onto a spreadsheet. The randomization sequence spreadsheet, randomization assignment sheet, and envelope will be kept and maintained a [REDACTED], which will be secure and accessible only by [REDACTED] staff and the nursing staff.

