5 STUDY POPULATION AND DURATION OF PARTICIPATION

5.1 Inclusion Criteria

Part 1:

1. Adult age ≥ 40 years old
2. Generally healthy without a current foot or ankle injury
3. No history of diagnosed vascular disease including: DVT, PE, VTE, peripheral vascular disease, post-phlebitic syndrome, or chronic venous insufficiency.
4. Mentally alert and understand English proficiently.
5. Able to give informed consent.

Part 2:

1. Adult age ≥ 18 years old
2. Admitted to Penn Presbyterian Medical Center.
3. Anticipated decreased level of mobility for at least 6 hours as determined by the clinical team in collaboration with [REDACTED].
4. Mentally alert and understand English proficiently.
5. Able to give informed consent.

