5.2 Exclusion Criteria

Part 1:

1. Injury to the lower limbs
2. Skin breaks, abrasion, or irritation in the area of the limb in contact with the OsciPulse device

Part 2:

1. Inability or contraindication to applying IPC to both legs
 - o Evidence of bone fracture in lower extremities
 - o Burns in the lower extremities, lacerations, ulcers, active skin infection or dermatitis, & ischemic limb in the legs at the site of IPC placement
 - o Acute ischemia in the lower extremities
 - o Severe peripheral vascular disease
 - o Amputated foot or leg on one or two sides
 - o Compartment syndrome
 - o Severe lower extremity edema
2. Subjects anticipated to require surgical intervention within six (6) hours of admission
3. Subjects with history of VTE (DVT or PE)

4. Previous vascular surgery
5. Pregnancy or within 6 weeks of postpartum period
6. Limitation of life support, life expectancy < 7 days or palliative care
7. Admitted to an outside hospital more than 24 hours prior to screening
8. A head-unit is unavailable for the 6 hours or more
9. At the discretion of the attending physician and / or clinical team, the subject's participation in the study is believed not to be in the best interest of the subject.

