7.3.2 Part 2 Hour 1-3

- Application of OsciPulse device (Group A) or IPC device (Group B)
-
- Hemodynamic ultrasonography (when feasible)
- Questionnaire assessment at the end of 3 hours
- Adverse Events
- Laboratory Results

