9.2.7 Safety Analysis

All subjects entered into the study and randomized at the baseline visit will have detailed information collected on adverse events for the overall study safety analysis

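### Part 2 randomises at screening, with no limit on the wait to the first device and no eligibility recheck at hour 0, so losses during the wait use up sequences and can unbalance them

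*Combined protocol and SAP*

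**What the plan says.** In the Part 2 schedule (section 7, Figure 3), the rows "Review inclusion/exclusion criteria" and "Randomization of treatment sequence" are each marked once, in the screening column, which is labelled as 24 hours before hour 0. Section 7.2 lists both under screening and enrolment. The schema (section 1.2) makes this Visit 1, "Screen, consent, and randomize eligible participants (within 24 hours from hospital admission"), and starts the first intervention at Visit 2.

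Section 7.3.2, the first device period, opens with applying the device. Neither it nor the rest of section 7.3 contains an eligibility step.

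Section 4.4 ties the sequence to enrolment: "When a subject is enrolled, the subject will be assigned a study identification number and the CRC will select the envelope" bearing that number. Envelopes are prepared in blocks of four for subjects 1 to 20. Nothing says what happens to an envelope whose subject never starts a device.

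Two Part 2 criteria look ahead over a 6-hour window: "Anticipated decreased level of mobility for at least 6 hours" (section 5.1) and "A head-unit is unavailable for the 6 hours or more" (section 5.2). Neither says from what moment the 6 hours run.

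**The concern.** Both forward-looking criteria matter at the moment the first device is applied, yet they are formally judged once, at an earlier visit, with no stated limit on how much earlier. Mobility, head-unit availability and the condition of the legs can all change in between. Section 9.2.3 itself names discharge and unexpected surgery among the events it expects to remove subjects.

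A loss between randomisation and hour 0 differs from a loss during the study window because it is avoidable: had the envelope stayed sealed, the subject would simply have been a screen failure. As written, that subject takes a sequence out of a small fixed set. The allowance in section 9.2.3 does not count the loss. The replacement rule in section 5.5 is at the sponsor's option and is worded for someone who has already started the clinical protocol, so it is unclear whether it applies.

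The sequence is also known during the wait, in a study that section 6.6 says is not blinded. Losses before hour 0 therefore need not be unrelated to which device comes first.

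**Working it through.** **The plan's own figures.** Envelopes: 4 in the first block plus 4 further blocks of 4 gives 4 + 16 = 20, as section 4.4 says. Evaluable subjects: 20 − 6 = 14, as section 9.2.3 says. Both reproduce. (The 14 is already one below the minimum of 15 in section 5.5. That is a separate inconsistency.)

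**Added input.** Let w be the number of the 20 randomised subjects who never start a device. The documents give no value. I assume w from 0 to 4 to show the scale.

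**Numbers left.** If the section 9.2.3 allowance is also used in full and nobody is replaced, 20 − w − 6 remain.

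**Sequence balance.** Let τ be the device effect (OsciPulse minus IPC) and π the period effect (second period minus first). The expected within-subject difference is τ − π in Group A (OsciPulse first) and τ + π in Group B. Section 9.2.4 averages these differences without a period term, so the mean difference is expected to be

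τ + π × (nB − nA)/(nA + nB).

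With 10 and 10 the second term is zero. If all w losses fall in one sequence, its size among those who start is π × w/(20 − w).

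| w (assumed) | 20 − w − 6 | Worst case, w/(20 − w) |
|---|---|---|
| 0 | 14 | 0 |
| 1 | 13 | 1/19 = 5% |
| 2 | 12 | 2/18 = 11% |
| 3 | 11 | 3/17 = 18% |
| 4 | 10 | 4/16 = 25% |

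**How likely is imbalance by chance?** Suppose the losses are unrelated to sequence and are drawn at random from 10 A and 10 B.

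- w = 2: both come from the same sequence with probability 2 × C(10,2)/C(20,2) = 90/190 = 0.47.
- w = 4: a 2–2 split has probability C(10,2)²/C(20,4) = 2025/4845 = 0.42, so the sequences differ by 2 or more with probability 0.58. All four come from one sequence, the 25% case, with probability 2 × 210/4845 = 0.09.

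Unrelated losses favour neither sequence on average, so they cause imbalance in a given trial but no systematic bias. Systematic bias needs losses that depend on the sequence, which an opened envelope makes possible.

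**The case against.** The strongest reply is that the wait may be trivial. A reader might infer from the Figure 3 column label that subjects wait up to 24 hours for the first device. The documents do not establish that. The schema counts its 24 hours from hospital admission, and section 5.3 likewise places screening in the first 24 hours after admission. Section 5.4 gives participation as 6 consecutive hours, and section 10.3 has adverse-event reporting run from consent to completion at 6 hours. Those passages fit randomisation close to hour 0. This stands: the gap is undefined, not shown to be 24 hours. It does not answer the point that no limit and no recheck are stated.

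Second, the 6 hours in the two criteria can naturally be read as the study period itself. The clinical team may also exclude a subject at its discretion (section 5.2, item 9), and section 6.2 provides for the device to be taken off. These are partial safeguards, but none is scheduled at hour 0.

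Third, section 5.5 allows enrolment above 20. That may restore numbers, but its wording may not reach someone lost before hour 0, and section 4.4 prepares no sequence beyond subject 20.

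Fourth, every analysed subject receives both devices, so imbalance does harm only if there is a period effect. That is correct, and the documents give no estimate of one.

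**Conclusion.** The point holds as a correctable weakness in the order of procedures. Randomisation and the only eligibility review precede the first device by an unstated interval, and a loss in that interval uses up a sequence, falls outside the section 9.2.3 allowance and can unbalance the crossover. The 5% to 25% is a worst-case share of a period effect of unknown size. It rests on the assumed 1 to 4 losses, all from one sequence, and counts subjects who start; losses after hour 0 can unbalance the sequences further. If the wait is in practice a few minutes, the effect is close to nil.

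Two stronger inferences are not supported. One is a predicted loss rate, obtained by compounding the 6 of 20 over a longer wait: that figure is a ceiling the plan tolerates, not an observed rate, and the length of the wait is unknown. The other is that unexposed subjects lower an adverse-event proportion. Section 9.2.7 does say "All subjects entered into the study and randomized at the baseline visit will have detailed information collected on adverse events", but section 9.2.2 evaluates safety by the number of events while each device is worn, with no denominator, and section 9.3 excludes non-completers altogether. The conflict between 9.2.7 and 9.3 over who is in the safety analysis is a separate point.

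**What to change.** - In Figure 3 and sections 4.4 and 7.2, move randomisation to immediately before the first device, leaving consent and screening where they are. Bring the schema and the reference in section 9.2.7 to randomisation at the baseline visit into line.
- In section 7.3.2, add a first step: reconfirm the existing Part 2 criteria at hour 0, with the mobility and head-unit windows counted from hour 0, and then open the next envelope.
- Assign the subject ID at consent and a separate sequential randomisation number at hour 0, and number the envelopes by the latter. A subject who fails the recheck is then a screen failure whose envelope stays sealed for the next subject, and no two consented subjects share an ID.

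The cost is a protocol amendment and a later hand-over of the payment card, which sits in the envelope. The amendment should also name who opens the envelope: section 4.4 gives this to research staff, while section 6.7 speaks of clinical staff applying the device. The change does not prevent imbalance from losses after hour 0.

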7.1 Pre-screening

Part 2 only:

- Medical record review to determine subject eligibility

7.2 Screening and enrollment

Part 1:

- Informed consent
- Review inclusion / exclusion criteria
- Demographics

- Adverse Events

Part 2:

- Informed consent
- Review inclusion/exclusion criteria
- Medical record review & Demographics
- Vital signs
- Randomization of treatment sequence
- Adverse Events

7.3 Study Intervention Phase

7.3.1 Part 1 Hour 0-3

- Application of the OsciPulse device
- Adverse Event monitoring
- Hemodynamic ultrasonography
- Tolerability Questionnaire

7.3.2 Part 2 Hour 1-3

- Application of OsciPulse device (Group A) or IPC device (Group B)
-
- Hemodynamic ultrasonography (when feasible)
- Questionnaire assessment at the end of 3 hours
- Adverse Events
- Laboratory Results

7.3.3 Part 2 Hour 3(+-1)-6

- Application of IPC device (Group A) or OsciPulse device (Group B)
- Hemodynamic ultrasonography (when feasible)
- Questionnaire assessment at the end of 6 hours
- Adverse Events

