1 STUDY SUMMARY

Title	A phase 2, randomized study of the tolerability and safety of the OsciPulse device for the prevention of VTE
Short Title	OsciPulse tolerability trial
Phase	Phase 2
Methodology	Randomized, crossover study
Study Duration	4 months
Study Center(s)	Penn Presbyterian Medical Center
	Part 1:
	Primary
	
• To determine the tolerability of the OsciPulse device on healthy individuals.
	Secondary:
	
• To determine the hemodynamic impact of the OsciPulse device on venous blood flow.
	Part 2:
	Primary:
Objectives	
• To determine the tolerability and safety of the OsciPulse device• To evaluate device design with respect to initial clinical safety and device functionality.
	Secondary:
	
• To assess the compliance of the OsciPulse device compared to a standard intermittent pneumatic compression device.• To evaluate the ultrasonographic hemodynamic parameters of the OsciPulse device compared to a standard intermittent pneumatic compression device.

Number of Subjects	Part 1: Three (3) subjects at a single site. Part 2: Fifteen (15) to Twenty (20) subjects at a single site.
Study Population	Part 1: Adults age \geq 40 years healthy volunteers. Exclusion criteria include a current foot or ankle injury, current vascular disease. Part 2: Adults age \geq 18 years admitted to the hospital. Exclusion criteria include contraindications for pneumatic devices, current or previous DVT, and pregnancy.
Investigational Product	OsciPulse mechanical therapy device for the prevention of VTE
Participant Duration	Part 1: Up to 3 hours Part 2: Up to 6-hours in hospital
Description of Facilities	Part 1: Enrollments will take place in the [REDACTED] offices clinical research space. Part 2: Enrollments will take place at the Penn Presbyterian Medical Center (PPMC). [REDACTED] coordinators will conduct bedside data collection in the hospital setting, and chart reviews will be conducted in the [REDACTED] office space located on the [REDACTED] [REDACTED] [REDACTED] at PPMC. This office space is locked with a front door security code.
Reference therapy	Intermittent pneumatic compression device

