4.2.2 Study Intervention Phase

Part 1: Enrolled healthy subjects will have the OsciPulse device applied by study or medical personnel according to the OsciPulse Instructions for Use. The subject will wear the device for a maximum of 3 hours while laying down. At the end of the study period the subject will receive an ultrasound scan of the deep venous system of the thigh/groin region to measure hemodynamics at a venous valve during immobility and during use of the OsciPulse device. Finally, the subject will participate in a questionnaire evaluation of their comfort and experience with the OsciPulse device. Participants will be compensated at \$50/ hour for their participation.

Part 2: After informed consent is obtained, baseline demographic and clinical data will be collected. The subjects will be randomized with equal allocation to either of the two treatment sequence groups:

- Group A (OsciPulse device then standard IPC device)
- Group B (standard IPC device then OsciPulse device)

For group A, the OsciPulse device will be applied to the subject on both legs in the first 3 hours. The subject will wear the device for the maximum number of hours as possible up to 3 hours. The [REDACTED] research team inquire with the subject if the device was removed during the testing period.. During the 3-hour period the study team will monitor for adverse events and a hemodynamic ultrasonography may be performed (when feasible) following the Ultrasound SOP. After 3 hours, the subject will complete the questionnaire evaluating the tolerability and safety of the device. In the following 3 hours, the standard IPC will be applied. Subjects will undergo the same procedure for compliance monitoring, adverse event monitoring, hemodynamic ultrasonography (when feasible), and questionnaire evaluation.

For group B, the same procedure will be performed but with the standard IPC in the first 3 hours and the OsciPulse device in the next 3 hours.

Participants will be compensated \$100 for their participation.

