9 STATISTICAL PLAN

9.1 Part 1

Part 1 of the trial is designed to test the tolerability of the OsciPulse system on healthy subjects for 3 hours prior to the 6-hour trial on patients. This is to determine if there are any immediate comfort issues that can be addressed prior to use in the clinical setting. Healthy volunteers are not the target population for the OsciPulse device and will have different tolerability for discomfort than hospital patients, but we feel that this test will be a qualitative analysis of the product prior to use in the target population. Subjects will indicate if the device caused 1) no discomfort, 2) mild discomfort, or 3) significant discomfort. **We will require that all three subjects indicate that there was not “significant discomfort” as reported on the subject questionnaire before continuing to Part 2.** This will be confirmed by the monitor prior to continuation to Part 2.

9.2 Part 2

Part 2 of the trial is designed to assess the tolerability and hemodynamic efficacy of the OsciPulse device in the clinical setting. The Primary endpoint is tolerability, which will be evaluated with questionnaires scored with a visual analog scale and will be directly compared between the OsciPulse device and a reference therapy device. Evaluable subjects will have completed the 6-hour study time that includes 3 hours with both therapies. This allows for the comparison between the therapies that makes the data quantitative rather than subjective. We will further measure hemodynamic efficacy through vascular ultrasound measurements of venous flow

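### Part 2's start window for the second device conflicts with the fixed end at hour 6 and the requirement of 3 hours on each device; only a switch at hour 3 meets every stated rule

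*Combined protocol and SAP*

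**What the plan says.** The procedures for the second Part 2 period carry the heading "7.3.3 Part 2 Hour 3(+-1)-6". The Figure 3 column for that period shows the same window. The list under the heading places the rating of the second device at a fixed time: "Questionnaire assessment at the end of 6 hours". Section 7.3.2 and Figure 3 place the rating of the first device at hour 3, also without tolerance.

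The other sections describe two adjoining 3-hour blocks:

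- Section 4.2.2, on wear: "The subject will wear the device for the maximum number of hours as possible up to 3 hours". For Group A's second period: "In the following 3 hours, the standard IPC will be applied". Group B follows the same procedure in reverse order.
- Section 5.4: "The duration of study participation will continue for 6 consecutive hours". The study summary gives the same total as a maximum: "Part 2: Up to 6-hours in hospital".
- Section 9.2: "Evaluable subjects will have completed the 6-hour study time that includes 3 hours with both therapies".
- Section 9.3 limits the analysis to subjects with the required exposure to both products, does not state that exposure in hours, and leaves out subjects who do not complete the requirements.

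The first period is also labelled in two ways. Its section heading is "7.3.2 Part 2 Hour 1-3", while Figure 3 starts it at hour 0.

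**The concern.** The schedule gives the start of the second period a tolerance, but gives none to its end, to either questionnaire or to the evaluable rule. A site can therefore switch within the permitted window and still produce a subject who does not have 3 hours on each device.

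Three things are at stake. First, the primary endpoint (section 9.2.1) compares visual analogue ratings of the two devices within a subject, and those ratings could follow different lengths of exposure. Section 4.2 itself justifies 3 hours as the time subjects need to give useful feedback. Second, after an early switch the hour-3 rating of the first device is given when the subject is already wearing the second. Third, it is unclear whether such a subject belongs in the analysis. In an unblinded trial (section 6.6) that should be settled before responses are seen.

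**Working it through.** **Inputs.** Second-period start t between hour 2 and hour 4 (section 7.3.3 and Figure 3; the unit of the 1 is not written and is taken as hours). End at hour 6 (sections 5.4 and 7.3.3). Ratings at hours 3 and 6 (sections 7.3.2 and 7.3.3, Figure 3). Wear of at most 3 hours per device (section 4.2.2). Evaluable rule of 3 hours on each device (section 9.2).

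**The plan's own figure.** 3 h + 3 h = 6 h. This uses the whole participation time and leaves 6 − 6 = 0 minutes to complete the first questionnaire, remove one device and fit the next.

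**Formulas.** Time available for the first device is t, and for the second 6 − t. With the wear limit, exposure is min(t, 3) and min(6 − t, 3). The shorter exposure is 3 − |t − 3|, and the capped difference is |t − 3|.

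| Second device starts | Available, first / second | With the 3-hour limit | 3 h on both? |
|---|---|---|---|
| hour 2 | 2 h / 4 h | 2 h / 3 h | no |
| hour 2.5 | 2.5 h / 3.5 h | 2.5 h / 3 h | no |
| hour 3 | 3 h / 3 h | 3 h / 3 h | yes |
| hour 3.5 | 3.5 h / 2.5 h | 3 h / 2.5 h | no |
| hour 4 | 4 h / 2 h | 3 h / 2 h | no |

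The largest capped difference is 1 hour, a ratio of 3/2 = 1.5. Read literally, even a 5-minute shift leaves one device at 2 h 55 min.

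**Timing of the ratings.** With a switch at hour 2, the first device is rated 3 − 2 = 1 hour after the change, with the second in use. With a switch at hour 4, the second device is rated after 6 − 4 = 2 hours, whereas the first was rated at hour 3 after up to 3 hours.

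**Does running the second period for a full 3 hours help?** It would end at t + 3, between hour 5 and hour 7. The late case passes the 6-hour limit of section 5.4. The early case still leaves only 2 hours on the first device.

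**Does the imbalance favour one device?** Suppose a shortfall of d hours on the second device shifts its rating by an amount b. The difference OsciPulse minus IPC then moves by −b in Group A, where IPC is second, and by +b in Group B. With equal numbers the mean shift is (−b + b)/2 = 0, but the spread of the paired differences increases. The paired t-test in sections 9.2.1 and 9.2.4 has no period term to remove that component.

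**The case against.** The strongest defence is that section 9.2 is being read too literally. Section 4.2.2 asks for wear as long as possible up to 3 hours, section 6.2 has the device removed when the subject walks or needs care, and section 4.6.2 makes percentage of time worn an endpoint. That endpoint would be close to 100% in everyone analysed if evaluability demanded 3 full hours of wear. On this view the rule means completing two assigned periods, and a switch inside the stated window is compliant. This is a plausible intention, and it is why exclusion of such subjects cannot be asserted. It does not settle the matter: with hour 6 as the end, a second period assigned from hour 4 is still only 2 hours long, and section 9.2 says 3.

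It can also be said that hour 6 is nominal, since section 4.2.2 defines the second period by its length. That rescues late switches only, and conflicts with section 5.4.

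Four stronger readings are tempting but not supported:

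- **A 2-hour against 4-hour exposure, ratio 1:2.** Those are the times available. The wear limit in section 4.2.2 caps exposure at 3 hours, so the extreme is 2 against 3.
- **Subjects who follow the schedule will be dropped.** They may be. Section 9.3 gives no hours, so a switch within the window could count as compliant.
- **Timing losses use up the 6 subjects allowed for in section 9.2.3.** That allowance is for clinical events such as discharge or unexpected surgery. Section 5.5 lets the sponsor replace non-evaluable subjects, even beyond 20 enrolled.
- **The comparison is biased towards one device.** Sequence is randomised 1:1 in blocks (section 4.4), so a period-linked shortfall falls about equally on both. Bias would need switch times that differ by sequence, or unequal sequences among those analysed. The documents show neither.

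**Conclusion.** The inconsistency is real and should be corrected. On the documents' own figures, a permitted start at any time other than hour 3 cannot give 3 hours on each device by hour 6, and no section reconciles the two. The size is at most 2 hours against 3, with the first device rated up to 1 hour after an early switch. The likely effect on the tolerability comparison is extra noise and a difference linked to period. Treatment of the affected subjects under sections 9.2 and 9.3 is ambiguous, and replacement limits any loss of numbers.

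This rests on reading the window in hours, taking hour 6 as the end, and applying the 3-hour wear limit to both devices. The documents do not say how often switches will fall away from hour 3, so the number of subjects affected cannot be calculated. Some delay is to be expected, because the changeover has no time of its own and section 6.7 asks staff to confirm the first OsciPulse inflation.

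**What to change.** - Reconcile Figure 3 and sections 7.3.2 and 7.3.3 with sections 4.2.2, 5.4, 9.2 and 9.3 so that one window and one set of period labels apply throughout. The choice of window and duration is the sponsor's.
- Give the evaluable definition (section 9.2) and the protocol-compliant definition (section 9.3) the same stated tolerance, fixed before any responses are seen.
- Time each questionnaire from the actual start of the device it rates, so that both devices are rated after the same elapsed time.
- Record actual on and off clock times for each device, and report exposure by device and by period. Section 8.8 already collects the reason for and length of interruptions that subjects report; the start and stop times are the new item.

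The cost is wording changes in the sections named and clock-time fields on the case report form. No extra subjects or procedures are needed.
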